DSGP Intervention and Outcome Measures. Participants will ingest 3,712mg (*i.e.*, six capsules) of DSGP, or placebo capsules, daily for eight weeks (+/-4 days). *Capsules should be swallowed and not crushed and ingested with meals (3 capsules every 12 hours).* DSGP, commercially available as Endocalyx™ (Microvascular Health Solutions LLC, Alpine, UT), include glucosamine sulfate, fucoidan, superoxide dismutase, and high molecular weight hyaluronan. An ongoing study using DSGP in chronic kidney disease patients (NCT03889236), to our knowledge, has not reported serious adverse side effects (*see enclosed letter from [name] and [name]*). Results from our pre-clinical studies in diabetic mice treated with DSGP (100mg/kg/day) for four weeks support that the proposed dosing regimen in humans will be capable of restoring the glycocalyx, particularly when considering the dose conversion from mouse to human. The use of Endocalyx in this study is filed under the research IND 164629 that was submitted on 11/23/2022.

[figure not shown]

Figure 2. Experimental design in Aim 1. DSGP, dietary supplementation of glycocalyx

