- Systematic review of charts from primary care and endocrinology clinics with previous approval from the different providers.
- Advertisement in social media outlets, local radio and TV stations.
- Submission a search request to the VA data warehouse (VINCI) for a listing of patients at the Harry S. Truman VA who have a diagnosis of T2D and are within the targeted age range and fulfil inclusion/exclusion criteria.

Screening Procedures:

Interested participants will be instructed, via letters, flyers, or via VA patient portal to contact study coordinator for a 10-minute interview (using a waiver of documentation of consent approved by the local IRB). The interview will be conducted with the goal of determining eligibility (demographics, height, weight, current medical illnesses/ medical history, and use of medications will be obtained). If a subject expresses interest to participate in the study, a screening visit will be scheduled.

Participant Compensation:

We have completed multiple clinical studies involving human subjects with adherence rates of greater than 95% and subject retention rates of greater than 85%. We utilize a validated retention strategy published by Jeffrey et al (Am J Clin Nutr. 2003;78(4):684-689) that has been successful. With respect to subject honoraria, subjects will be paid \$25 after completion of the screening visit, \$75 after the baseline visit, and \$255 after the final visit. Subjects will also receive travel compensation of \$0.41/mile

traveled (round trip) from their residence to the Harry S. Truman VA Hospital and Clinics for each of their study visits. If subjects are asked to repeat safety labs, you will be compensated for applicable travel at a rate of \$0.41/mile traveled (round trip) from their residence to the Harry S. Truman VA Hospital and Clinics. Thus, a total compensation of \$355 plus applicable travel compensation will be provided as study events are completed. Participants will receive study compensation via check.

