5.4 Inclusion/Exclusion Criteria

Inclusion:

- 1) 45-74 years of age at the time of enrollment
- 2) Diagnosis of T2D by a health care provider, confirmed by chart review
- 3) HbA1c <9% and fasting blood glucose <200 mg/dL at screening visit
- 4) Body mass index (BMI) 25–45 kg/m²
- 5) Women should be postmenopausal (absence of menses for at least 1 year)
- 6) Sedentary subjects (<2 days/week of vigorous exercise)
- 7) Willingness to follow up instructions provided by study team

Exclusion:

- 1) Evidence of cardiac arrhythmias, unstable angina (or other cardiac event), heart failure or stroke in the last 12 months
- 2) Evidence of chronic kidney disease stage IV or V (GFR <30 mL/min)
- 3) Evidence of uncontrolled hypertension, systolic blood pressure > 180 mmHg and/or diastolic blood pressure > 110 mmHg on more than 2 occasions in the past 12 months or at screening visit
- 4) Diagnosis of chronic liver disease
- 5) Uncontrolled thyroid dysfunction (abnormal TSH within 3 months of study enrollment)
- 6) Active cancer
- 7) Current use of hormone replacement therapy
- 8) Excessive alcohol consumption (>14 drinks/week for men, >7 drinks/week for women)
- 9) Current pregnancy or intent to become pregnant during the course of the study
- 10) Inability to swallow capsules
- 11) Known allergies to any of the compounds in the supplement: glucosamine extract, fucoidan extract, olive extract, artichoke extract, red and white grapes extract, melon concentrate, hyaluronic acid

	Screening Visit	AMBP Fitting (Day -7 to -2)	Pre- Assessment (Day 0)	Safety Blood Draw (Days 7-14)	Dosing Window (Days 1-56)	AMBP Fitting (Day 49-54)	Post- Assessment (Day 56)
Informed consent form signing	X						
Medical history	X						
Concomitant medication assessment	X		X		X	X	X
Height assessment	X		X				X
Weight assessment	X		X				X
Waist circumference assessment	X		X				X
Vitals signs (blood pressure, heart rate and respiratory rate, temperature)	X		X				X
12-lead ECG	X						
Fasted bloodwork: HbA1c, FLP, CMP, TSH, H&H	X						
Bloodwork: PT, PTT, H&H	X			X			X
3- Day food diary		X				X	
24-hour Ambulatory Blood Pressure Monitoring (AMBP)		X				X	
24-hour AMBP activity log		X				X	
AM T2D medication hold			X				X
AM Tobacco hold	X		X				X
24-hour exercise hold	X		X				X
Overnight fasting	X		X				X
Fasted blood draw			X				X
Glycocheck		X	X				X
Pulse Wave Velocity			X				X
Brachial FMD			X				X
Femoral FMD			X				X

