5.5 Study Evaluations

Screening and Consenting Visits:

This visit will last approximately 60 minutes in duration and will occur in the morning at the Endocrinology Clinic space at the VA Hospital. Subjects will be asked to come after an overnight fast before their arrival at the clinic. Subjects will be asked to avoid tobacco use on the morning of scheduled visits. Informed written consent will be obtained by [name] in a private environment. The decision to participate or not will not influence medical care by the co-PI or any other member of the team. After informed consent has been obtained, the following procedures will take place: 1) anthropometric measurements (waist circumference, height, body weight); 2) seated blood pressure measurements (in triplicate) after five minutes of rest, heart rate, temperature, and respirations 3) resting 12-lead ECG; 4) phlebotomy to obtain blood sample for serum chemistries, HbA1c, lipid panel, thyroid, liver, kidney function, hemoglobin and hematocrit and coagulation tests (prothrombin time, and activated partial prothrombin time). Once screening tests have been completed and resulted, enrollment eligibility will be reviewed by co-PIs, [name] and [name].

Eligibility:

Eligible subjects will be scheduled for four outpatient study visits (2 equipment fitting visits-1 hour duration each, and pre- and post-treatment assessment, eight hours duration each) at the Clinical Translation Science Unit (CTSU) of the University of Missouri, a core facility and one outpatient study visit at the Harry S. Truman VA Hospital (safety labs). The first study visit will be scheduled within four weeks of the screening visit. Participants will be instructed to maintain their habitual physical activity levels and dietary habits throughout the eight-week period. Adherence to the supplement/placebo will be facilitated (and documented) by the following processes: 1) the study coordinator/research nurse will review proper adherence directions at baseline visit; 2) capsule boxes will be provided at the baseline visit and the participant will be asked to bring the box at the post-treatment visit to count any remaining capsules; and 3) participants will be contacted on a weekly basis by the study coordinator to check in and review compliance.

Equipment fitting visits and potential risks:

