5.6 Data Analysis

For Aim 1 of the study, twenty-four subjects (**n=24**) will be enrolled in the DSGP/placebo treatment with 12 subjects randomized to each group. For Aim 2 of the study, seventy-two subjects (**n=72**) will be enrolled with eighteen subjects randomized to each of the four interventions.

Statistical analysis, sample size and power calculations:

Aim 1: We will analyze change in PBR (and change in other secondary outcomes) using ANCOVA with baseline PBR as a covariate and dietary supplement as a main effect. We will use residual diagnostic plots to check for violations of assumptions on normality and equal variance among groups. If variance is not equal, separate variance components can be estimated in SAS mixed procedure to account for these differences. Inspection of the variance estimates and a likelihood ratio test can validate the need for this approach. Transformation may be used to correct for skewness and unequal variance. This analysis has two treatment levels to contrast and no need for multiple contrast correction like Bonferroni.

Power estimates are based on preliminary data in PBR (for Aim 1) and FMD (for Aim 2). We observed a mean of 1.742 (standard deviation, SD=0.27) and 1.45 (SD=0.20) in PBR for type 2 diabetes (T2D) and healthy subjects, respectively. Based on our findings in the pre-clinical mouse model of T2D that glycocalyx thickness was completely restored with DSGP, we predict that DSGP in T2D subjects will cause a mean decrease in PBR of 0.3, with no changes in response to placebo. As presented in Figure 3E, we observed a mean of 3.78 (SD=1.86) and 7.06 (SD=2.21) in FMD for T2D and healthy subjects, respectively. We predict that DSGP + exercise will cause a mean increase in FMD of 2, which represents two-thirds of the distance between healthy and T2D subjects. Our pilot data was also

used to estimate the within-subject variance, assuming a correlation of $r=0.6$ between serial measurements on the same subject.

For Aim 1, assuming pre-treatment PBR $SD=0.27$, post $SD=0.20$, and correlation between pre and post is 0.6 , then the SD of the pre to post treatment change in PBR is 0.22 . A sample size of $n=10$ per group will provide 82% power when the true mean difference in PBR change is 0.3 . Adjustment of sample size for 20% attrition results in 24 subjects (12 per group) for Aim 1 and 72 subjects (18 per group) for Aim 2.

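### Section 5.4 excludes allergy to the supplement's components but not their use, and nothing bars starting them during the trial, so the DSGP–placebo difference in PBR could be attenuated

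*Combined protocol and SAP*

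**What the plan says.** - **Eligibility (5.4).** Of the eleven exclusions, only the last concerns the supplement's ingredients: "Known allergies to any of the compounds in the supplement". Section 5.5 repeats the allergy exclusion in its paragraph on the supplement and adds nothing about use. Exclusion 7 bars current use of hormone replacement therapy, so the protocol does exclude on current use elsewhere.
- **The product (5.1).** DSGP is "commercially available as Endocalyx", and its contents "include glucosamine sulfate, fucoidan, superoxide dismutase, and high molecular weight hyaluronan".
- **Conduct during treatment (5.5).** "Participants will be instructed to maintain their habitual physical activity levels and dietary habits throughout the eight-week period". Supplements are not mentioned. The weekly call reviews compliance with the study capsules.
- **Recording.** The pre-screening interview in 5.2 says that "use of medications will be obtained". Table 1 in 5.4 lists "Concomitant medication assessment" at screening, Day 0, the dosing window, the second blood pressure monitor fitting and Day 56. Neither place names supplements or says what follows if use is found.
- **Power (5.6).** The calculation predicts that "DSGP in T2D subjects will cause a mean decrease in PBR of 0.3, with no changes in response to placebo". It takes the SD of change as 0.22 and reports 82% power with 10 per group.

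**The concern.** Aim 1 asks what these precursors do to PBR compared with not taking them. That contrast is clean only if subjects arrive unexposed and the placebo arm stays unexposed. As written, someone already taking the commercial product, or a product sharing its components, can be randomized.

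There are two separate routes to a smaller difference:

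1. An existing user assigned to DSGP may have little further response, which pulls the DSGP mean toward zero.
2. A placebo subject who starts such a product during the eight weeks may improve, which pulls the placebo mean toward the DSGP arm.

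With 10 completers per arm, a single subject is 10% of an arm. The problem is also hard to repair later: dropping users after randomization reduces a sample of 24 and gives up the protection of randomization.

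**Working it through.** **Inputs from section 5.6.** Pre-treatment SD 0.27, post-treatment SD 0.20, correlation 0.6, difference in PBR change 0.3, 10 completers per group. Alpha and sidedness are not stated. Two-sided 0.05 is assumed because it reproduces the plan's figure.

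**Reproducing the plan.** SD of change = √(0.27² + 0.20² − 2 × 0.6 × 0.27 × 0.20) = √0.0481 = 0.2193, rounded to 0.22. A two-sample t-test with 18 df has noncentrality 0.3 / (0.22 × √(2/10)) = 3.05, which gives power 82.2% (82.4% with the unrounded SD). The stated 82% is therefore a change-score t-test figure.

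**The planned analysis.** Section 5.6 specifies ANCOVA adjusted for baseline PBR. On the same inputs the residual SD is 0.20 × √(1 − 0.6²) = 0.16, with 17 df. Power at a difference of 0.3 is 97.6%.

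**Dilution model (assumption).** Let f be the share of the DSGP arm who are existing users, and k their response relative to non-users. The expected difference is 0.3 × [1 − f(1 − k)]. The documents give neither f nor k, so a range is shown with 10 per arm. The t-test columns use SD 0.22.

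| f | Difference, k = 0 | t-test, k = 0 | t-test, k = 0.5 | ANCOVA, k = 0 |
|---|---|---|---|---|
| 0 | 0.300 | 82.2% | 82.2% | 97.6% |
| 5% | 0.285 | 78.2% | 80.3% | 96.3% |
| 10% | 0.270 | 73.7% | 78.2% | 94.4% |
| 20% | 0.240 | 63.6% | 73.7% | 88.5% |

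**Extra variance.** A mix of responders and non-responders also widens the spread in the DSGP arm. Adding f(1 − f) × 0.3² / 2 to the pooled variance (k = 0) gives t-test power of 76.5%, 70.3% and 57.7%, and ANCOVA power of about 95%, 91% and 80%, at 5%, 10% and 20%.

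**All randomized subjects complete.** With 12 per arm, t-test power is 89.1% with no users, 81.9% at 10% and 72.4% at 20% (k = 0, SD 0.22).

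**Placebo route.** If a share g of the placebo arm starts a product and gains the full effect, the difference is 0.3 × (1 − g), so the k = 0 columns apply with g in place of f. This is an upper bound, because a subject who starts partway through is exposed for less than eight weeks.

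**The case against.** The strongest reply is that the gap is in the wording and its effect is speculative. Several parts of that reply stand.

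- **Prevalence and non-response are unknown.** Nothing in the documents says how many candidates use these products or that users respond less. DSGP is a four-component product, and taking one component alone need not use up the response to the combination. Zero response is the extreme case, which is why the half-response column is shown.
- **The planned ANCOVA has margin.** A reader might infer that the trial's analysis falls from 82% to 64% power. That is not supported: those figures belong to the change-score t-test, and ANCOVA on the plan's own inputs stays near 88% even at 20% non-responding users. The margin does depend on r = 0.6 and on a full 0.3 effect extrapolated from mice. If the true effect were 0.2 (an assumption), ANCOVA power would be 75% with no users and 66% at 10%. Adjustment also does not undo the shrinkage of the estimate.
- **Stable users on placebo do no harm to the contrast.** A reader might infer that prior use contaminates both arms. A stable user on placebo should show no change, as 5.6 assumes. The placebo route needs someone to start a product during the trial.
- **The habit instruction does not name supplements.** A reader might infer that the protocol tells users to keep taking them. It speaks of physical activity and diet only. Read broadly enough to cover supplements, it would equally discourage starting one.
- **Use might be detected.** Medication questions, food diaries, weekly calls and the co-PIs' eligibility review could all bring it to light. But no rule says what to do then, and a user who reports it still meets 5.4.

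**Conclusion.** The gap is real: followed as written, the plan can randomize current users of the product or its components, and nothing restrains new use before the post-assessment. The supported conclusion is that the DSGP–placebo difference could be attenuated, not that it is. The consequence is an effect estimate biased toward zero, with loss of power. Stable prior use is expected to balance between arms apart from chance, so it gives no reason to expect a spurious benefit.

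The size rests on an assumed share of users and an assumed response among them. At 10% users in the DSGP arm (one of ten completers), the expected difference falls from 0.30 to 0.27 with no response, or to 0.285 with half response. The corresponding change-score power is 74% or 78%; ANCOVA power with no response is 94%. This is a modest weakness that should be closed before enrolment because closing it is cheap. It does not show that Aim 1 is underpowered.

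**What to change.** 1. Add to 5.4 an exclusion for current or recent use of DSGP or of products containing its active components, with the look-back interval set by the sponsor.
2. Add to the participant instructions in 5.5 that no such product is to be started before the post-assessment visit.
3. Ask about these products by name at the pre-screening interview, at each concomitant-medication assessment and at the weekly call.

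No new visit, test or change in sample size is needed. The cost is protocol wording, a few otherwise eligible subjects and a slightly narrower sample. Section 5.2 cites 9,400 primary care patients with T2D and 1,476 seen in the Endocrinology Clinic (the two groups may overlap), against 24 places in Aim 1. If users turned out to be common, the recruitment cost would rise, but so would the attenuation avoided.

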5.0 Study Procedures (*Proof of Concept Clinical Trial Phase*)

5.1 Study Design

Aim 1 (*Proof of Concept Clinical Trial Phase*): Document that DSGP enhances endothelial glycocalyx integrity in Veterans with T2D.

Rationale. Based on our preliminary data showing that DSGP augments endothelial glycocalyx thickness and vasodilatory responses in a mouse model of T2D (**Figure 2**), the purpose of this Aim is to demonstrate that these effects are applicable to Veterans with T2D. Importantly, our results should establish for the first time that glycocalyx restoration is accompanied by improvements in endothelial function, providing support for our proposal that the glycocalyx is a key therapeutic target to combat vascular complications in diabetes. Finally, the results obtained in Aim 1 will set the stage for an expansion of the clinical trial (Aim 2) designed to elucidate if restoration of the endothelial glycocalyx enhances exercise training-induced vascular adaptations in T2D subjects.

Hypothesis. We hypothesize that DSGP will enhance endothelial glycocalyx integrity in T2D subjects and that this effect will be associated with increased shear stress mechanotransduction and endothelial function.

Study Design and Recruitment of Participants. We will employ a double-blinded randomized placebo control trial designed to determine the effects of DSGP on endothelial glycocalyx integrity and endothelial function

(**Figure 9**). Veterans diagnosed with T2D (n=24), 45- 74years of age, will be recruited from the Harry S. Truman Memorial VA Hospital in Columbia, Missouri. The selected age range aligns with data from the Centers for Disease Control, indicating that the incidence of T2D in Veterans continues to increase after even after 65 years of age.⁴ Subjects will be classified as having T2D based on physician diagnosis, following the American Diabetes Association guidelines.⁵¹

Randomization and Blinding. Participants will be assigned to DSGP or placebo using block randomization to achieve balance in the allocation of participants to treatment arms. Randomization order will be provided to the investigational pharmacy for intervention allocation. Preparation and administration of the supplement/placebo capsules will be directed by the VA Hospital Investigational Pharmacy. All members of the investigative team involved in data acquisition and analysis will be blinded to group assignment, and subjects will not be informed of their group status.

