Insulin and glucose infusion with leg blood flow, sphygmomanometry, and beat- to-beat via finometer			X				X
Contrast enhanced ultrasound			X				X
DEXA			X				X
Supplement/placebo dispensing			X				
Daily Supplement/Placebo dosing					X		
Weekly phone check-in					X		

Table 1. Schedule of study activities. Note that after screening visit, once eligibility has been confirmed subject will be randomized.

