In the week leading up to the pre and post assessment visits, the subjects will attend an appointment with the purpose of being fitted with an ambulatory blood pressure monitor. The subjects will be instructed on the wear and use of the ambulatory blood pressure system and will take the equipment with them for home use over a 24-hour period. Subjects will also be instructed on the use of the Glycocheck equipment and practice collecting measurements.

Ambulatory blood pressure monitoring: Blood pressure monitoring will be conducted with a Welch Allyn ABPM 7100 Ambulatory Blood Pressure Monitor or equivalent device and adult blood pressure cuff. This procedure is not standard of care. This procedure poses no risks but may cause some discomfort due to cuff inflation.

Assessment visits and potential risks:

At each CTSU visit, subjects will arrive after an overnight fast, having not taken medications the morning of the study, and not exercised for 24 hours. Subjects will be asked to avoid tobacco use on the morning of scheduled visits. Anthropometric (waist circumference, height and body weight), body composition (via DEXA) and blood pressure measurements will be obtained. At this time, a three-day dietary recall will be performed by a registered dietitian at the CTSU and analyzed using NDSR software. Subsequently, subjects will be placed supine in a quiet, climate-controlled room (22–23°C) for measurements to be performed are described below.

Time point	Blood volume (mL)
Screening	20
Baseline visit	70
Safety visit	10
Final Visit	80
Total	180
*Unscheduled safety labs (10)	

Box 1. Expected blood draw volumes during the duration of the study.

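### Does it matter that no randomisation day is given relative to the Day 0 baseline, and that one exclusion sits outside the 5.4 list?

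*Combined protocol and SAP*

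**What the plan says.** Section 5.1 describes block randomisation, with the order held by the investigational pharmacy, and says nothing about the day. Table 1 has no randomisation row. Its note supplies a trigger: "Note that after screening visit, once eligibility has been confirmed subject will be randomized".

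Section 5.5 describes how eligibility is settled: "Once screening tests have been completed and resulted, enrollment eligibility will be reviewed by co-PIs". It continues: "Eligible subjects will be scheduled for four outpatient study visits", and "The first study visit will be scheduled within four weeks of the screening visit". The first of these visits is the blood-pressure fitting at Day -7 to -2. Table 1 marks dispensing only on Day 0. It marks Glycocheck at the first fitting visit, Day 0 and Day 56, and 5.5 presents the fitting-visit use as training: "Subjects will also be instructed on the use of the Glycocheck equipment and practice collecting measurements".

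Section 5.6 plans an ANCOVA of change in PBR with baseline PBR as covariate. It sizes Aim 1 at 10 per group for 82% power and raises this to 12 per group for 20% attrition.

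On radiation, the DEXA paragraph of 5.5 excludes anyone who had significant ionizing exposure from research or medical procedures in the previous 12 months. None of the 7 inclusion or 11 exclusion criteria in 5.4 mentions it. It is also not named in the telephone interview of 5.2, where "demographics, height, weight, current medical illnesses/ medical history, and use of medications will be obtained".

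**The concern.** Read in sequence, the text suggests that screening results come back, the co-PIs confirm eligibility, the participant is randomised, and only then do the fitting visit and Day 0 take place. Allocation would then precede baseline PBR and dispensing by at least two days and possibly by weeks.

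Anyone who drops out in that gap counts as randomised but contributes nothing to an ANCOVA that needs both a baseline and a follow-up value. Section 5.6 names no analysis population and no rule for such a person. With 24 randomised and 20 needed, there are four spare places, and losses before Day 0 could be avoided by allocating later.

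The radiation rule adds a related worry. A team screening strictly from the 5.4 list could randomise someone whom 5.5 excludes.

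**Working it through.** **1. The gap.** The latest fitting visit is Day -2, so allocation on confirmed eligibility before that visit falls at least 2 days before Day 0. If the first study visit is the fitting visit, screening to Day 0 can reach 28 + 7 = 35 days. Randomisation comes after results and review, so its own gap is shorter than 35 days. Nothing in the note rules out a gap of zero.

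**2. The plan's power.** Inputs from 5.6: pre SD 0.27, post SD 0.20, correlation 0.6, difference 0.3. The plan gives no alpha; two-sided 0.05 is assumed.
- SD of change = √(0.27² + 0.20² − 2 × 0.6 × 0.27 × 0.20) = √0.0481 = 0.219, stated as 0.22.
- At 10 v 10: SE = 0.22 × √(1/10 + 1/10) = 0.0984; noncentrality 0.3/0.0984 = 3.05; 18 df; power 82.2%. The stated 82% reproduces.

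**3. Attrition.** 10 × 1.2 = 12 per group, or 24, all described in 5.6 as randomised. The allowance therefore covers every loss after randomisation, whether before or after Day 0. Spare places: 24 − 20 = 4. In 5.2 the group reports "subject retention rates of greater than 85" percent, which means fewer than 24 × 0.15 = 3.6 losses, within the four. The starting point of that retention rate is not given.

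**4. Power as places are lost (two-sample t-test on change, SD 0.22).**

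| Completers | Power |
|---|---|
| 12 v 12 | 89.1% |
| 12 v 11 | 87.6% |
| 11 v 11 | 86.0% |
| 12 v 10 | 85.7% |
| 10 v 10 | 82.2% |
| 10 v 9 | 79.9% |

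Uneven loss of two costs 0.3 points (86.0% against 85.7%). Power drops below 80% only at the fifth loss, and then by 0.1 point.

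**5. Power under the planned analysis.** The primary analysis is ANCOVA. Residual SD = 0.20 × √(1 − 0.6²) = 0.16, with df = n₁ + n₂ − 3.

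| Completers | Power |
|---|---|
| 10 v 10 | 97.6% |
| 10 v 9 | 96.9% |
| 8 v 8 | 93.3% |
| 6 v 6 | 82.3% |

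This headroom depends on the post SD of 0.20. If the post SD stayed at 0.27, the residual SD would be 0.27 × 0.8 = 0.216, and power would be 83.3% at 10 v 10 and 81.0% at 10 v 9.

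**6. Validity.** Under 5.1, staff who acquire and analyse data are blinded and participants are not told their group. A PBR reading taken before any capsule cannot be affected by the assigned product, so it is a proper covariate even if allocation came first. Dropout before Day 0 cannot depend on knowing the arm, so it gives no systematic difference between arms.

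**7. Radiation.** The rule in 5.5 is mandatory as written. Section 5.3 and Table 1 require a medical history at screening, where the exposure can be asked about. The two sections differ in completeness; neither permits what the other forbids.

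**The case for a change.** The strongest case is that the margin is thinner than it looks. A literal 20% loss from 24 is 4.8, leaving 19.2 completers and 80.4% power on the change-score basis. If k participants were lost before Day 0 and 20% of the remainder dropped out later, power would be 78.5% for k = 1 and 76.5% for k = 2. Allocation immediately before dispensing would avoid those early losses without adding a visit, and stating the day would cost one line.

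The arithmetic is right, but it needs two things the documents do not supply: a loss rate before Day 0, and a 20% that applies on top of it. Section 5.6 applies the 20% to the randomised total. The figures also belong to the sizing test, while the planned ANCOVA is considerably more powerful under the same inputs.

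Later allocation is not clearly free either. Under 5.1, "Preparation and administration of the supplement/placebo capsules will be directed by the VA Hospital Investigational Pharmacy", whereas the Day 0 visit is at the university research unit. Numbered kits would have to be prepared ahead and held at another facility, and the documents do not say whether that can be done. This may be why allocation follows eligibility.

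Two smaller points stand. The visible text names no randomisation day and does not say how a participant who never receives capsules is reported. The radiation rule is indeed absent from 5.4.

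**Conclusion.** No change to the plan is called for. The missing day is a detail that the trial team and pharmacy have to settle in operation, and either answer gives a sound trial: allocation on Day 0 fits the note, and earlier allocation leaves a valid blinded comparison. Analysts would report participants never dispensed capsules by arm, and these people have no PBR change to analyse. The extra power cost is zero when the 20% is counted from the 24 randomised, as 5.6 reads, and the stated 82% stands. Moving allocation to Day 0 is a reasonable preference with no demonstrated gain. The radiation item is a clerical slip: the exclusion is already in the protocol and binds from 5.5, and copying it into 5.4 would be editorial tidying.

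This rests on two-sided 0.05, on the Day 0 Glycocheck being the baseline (an inference from its description as practice at the fitting visit), and on the visible text. The Aim 1 design figure is not reproduced and some pages were removed, so a randomisation point may be shown there.
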